For continuous-valued ADA titer, missing values prior to the last observed visit will be filled in with MCMC imputation to make the dataset monotone. Missing values after discontinuation will be imputed by regression imputation of the monotone missing dataset. If there are at least 6 retrieved dropouts in each treatment arm, then a pattern mixture model estimated from the retrieved values will be used for regression imputation of missing values. Otherwise, the complete case missing values method will be used. Missing values for the binary response variable will be imputed using a logistic regression multiple imputation model. A monotone missingness pattern will be created by taking a random draw from the binomial distribution with the same probability as the observed responses from the same treatment group at the same visit.

Pattern mixture models will be fit separately for ADA binary response and for ADA titer. Binary response will be imputed using a logistic regression imputation model, while ADA titer will use a continuous-valued regression. Independent variables in the regression will include the values at all prior visits. Each imputation will be repeated 30 times with a seed of 40872021 for ADA binary response and a seed of 41671703 for ADA titer. Code for the multiple imputation analyses is presented in Appendix 10.1.

If baseline value is missing, the missing baseline value will be imputed with six imputations based on binomial distribution using probability of no missing baseline values from same treatment group.

After imputation, the dataset containing the imputed visitwise TEAR positive or negative status binary response and the dataset containing the imputed ADA titer values will be merged by subject, visit, and imputation number. The Week 24 values will then be used to assign the status of TEAR positive or negative, as follows:

If the subject was ADA negative at baseline, then this subject will be considered TEAR positive if any post-baseline observed or imputed value was ADA positive; otherwise, the subject will be considered TEAR negative. The imputed titer values will not be considered in subjects who are ADA negative at baseline.

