 3. Run a pattern mixture model logistic regression to impute missing values to generate 30 imputed datasets. This will generate a single pooled dataset containing one observation per subject per imputation. All missing values will have been filled in for each subject.

Step 1.

The dataset for this imputation has to put the values for all weeks onto one record. That is, the dataset would have one record per subject, with 8 values for RESP0 and RESP8–RESP15. One way this can be accomplished is the following:

```
data analysis (keep=usubjid RESP0 RESP8-RESP14);
set indata;
by usubjid avisitn;
array R {9} RESP0 RESP8-RESP15;
retain RESP0 RESP8-RESP15;
if first.usubjid then do;
    resp0 = base;
    do visit = 8 to 15;
        R{visit} = .;
    end;
end;
do visit = 8 to 15;
    if avisit = visit then R{visit} = aval;
end;
if last.usubjid then output;
run;
```

STEP 2.

First a flag needs to be created to indicate which missing values need to be filled in. This is a visit-level variable for each subject. For explanatory purposes, this variable will be referred to as EMPTY_x for Visit x. For each visit where a subject has a missing value, use the logic below:

- If there is a non-missing value for any visit AFTER Visit x, then EMPTY_x=0;
- Else if there are no non-missing values for any of the remaining visits, then EMPTY_x=1;

Then all records with EMPTY_x=1 have to have their RESP_x value filled in with a randomly generated 0 or 1. One way this can be accomplished is the following:

```
/** step 2: Make missingness monotone */  
%global mylrate novrate;
```

```
%macro getrate(visnum);
```

```
    proc sort data=indata;  
        by trtgroup;  
    run;  
    ods exclude all;  
    proc freq data=indata;  
        by trtgroup;  
        table RESP&visnum;  
    ods output onewayfreqs=pct;  
    run;  
    ods exclude none;
```

```
    data binom;  
        set pct (where=(RESP&visnum=1));  
        probresp = percent/100;  
        if trtgroup="MYL-1601D" then call  
            symput("mylrate",probresp);  
        else if trtgroup="NOVOLOG" then call  
            symput("novrate",probresp);  
    run;
```

```
%mend getrate;
```

```
%macro fillin (visit);
```

```
    %getrate(&visit);
```

```
    data indata;  
        set indata;  
        if empty&visit=1 then do;  
            if trtgroup="MYL-1601D" then  
                RESP&visit=ranbin(86537043,1,&mylrate);  
            else if trtgroup="NOVOLOG" then  

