    resp0n resp8n resp9n resp10n resp11n resp12n resp13n
resp14n) ;
mnar model (resp8-resp15 / modelobs=ccmv(k=1));
run;
```

10.1.2 Multiple imputation for continuous ADA titer if baseline ADA positive.

For purposes of these specifications, let ADA_x represent the continuous value for ADA titer at Visit *x*, where *x* takes the values 0 (for Baseline) or 8–15. The seed that will be used in the multiple imputation of ADA titer will be 41671703.

There are 3 steps to this process:

1. Create a dataset with one record per subject, containing all values of ADA for all weeks (Baseline and Weeks 2–24 on one record); that is, each record would contain variables for ADA₀ and ADA₈–ADA₁₅. The subject-level RETRIEVED variable described in Section 8.7.2.1 can also be generated at this time for subjects who discontinued treatment, based on whether values after treatment discontinuation were retrieved (set retrieved=1) or remain missing (set retrieved=0).
2. Run 30 Markov Chain Monte Carlo (MCMC) imputations to make the missing

values in the dataset have a monotone missingness pattern. This will produce a dataset with an index variable `_imputation_` and otherwise the same variables as the input dataset. It will have one record per imputation per subject.

3. Run a pattern mixture model regression imputation on each imputed dataset from Step 2. This will generate a dataset with the same structure as the input dataset, but will have the missing values filled in.

Step 1.

The dataset for this imputation has to put the values for all weeks onto one record. That is, the dataset would have one record per subject, with 8 values for ADA0 and ADA8-ADA15. One way this can be accomplished is the following:

```
data analysis (keep=usubjid trtp ADA0 ADA8-ADA15);
set indata;
by usubjid avisitn;
array y {9} ADA0 ADA8-ADA15;
retain ADA0 ADA8-ADA15;
if first.usubjid then do;
    ada0 = base;
    do visit = 8 to 15;
        y{visit} = .;
    end;
end;
do visit = 8 to 15;
    if avisit = visit then y{visit} = aval;
end;
if last.usubjid then output;
run;
```

Step 2.

```
/** step 2: Create monotone missingness using MCMC
imputation */
proc mi data=analysis seed=41671703 nimpute=1
out=outdata1;
mcmc impute=monotone;
var ada0 ada8-ada15;
run;
```

Step 3.

```
/***/ step 3: Perform PMM regression imputation ***/  
proc sort data=outdata1;  
run;  
  
/***/ Code to use if >=6 retrieved subjects per arm ***/  
proc mi data=outdata1 seed=41671703 nimpute=30  
out=outdata2;  

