ods output parameterestimates=parms;  
run;  
  
proc print data=parms;  
var estimate stderr lclmean uclmean probt;
```

```
run;
```

10.1.4 Multiple imputation for HbA1c.

HbA1c is measured at baseline and at Weeks 12 and 24 (visits 11 and 15). For purposes of these specifications, let HB_x represent the continuous value for HbA1c value at Visit x, where x takes the values 0 (for Baseline) or 11 or 15. The seed that will be used in the multiple imputation of ADA titer will be 24637883. The imputations will be combined using a mixed model for repeated measures.

There are 6 steps to this process:

1. Create a dataset with one record per subject, containing all values of HbA1c for all weeks (Baseline and Weeks 12 and 24 on one record); that is, each record would contain variables for HB₀, HB₁₁, and HB₁₅.
2. Run 30 Markov Chain Monte Carlo (MCMC) imputations to make the missing values in the dataset have a monotone missingness pattern. This will produce a dataset with an index variable `_imputation_` and otherwise the same variables as the input dataset. It will have one record per imputation per subject.
3. Run a pattern mixture model regression imputation on each imputed dataset from Step 2. This will generate a dataset with the same structure as the input dataset, but will have the missing values filled in.
4. Transform the dataset back into one record per subject per visit, with imputation number retained on each record.
5. Run a mixed model for repeated measures on the imputed datasets.
6. Combine the imputations to provide summary statistics.

Step 1.

The dataset for this imputation has to put the values for all weeks onto one record. That is, the dataset would have one record per subject, with 3 values for HB₀, HB₁₁, and HB₁₅.

One way this can be accomplished is the following:

```
data analysis (keep=usubjid trtp HB0 HB11 HB15);  
set indata;  
by usubjid avisitn;  
array y {3} HB0 HB11 HB15;  
retain HB0 HB11 HB15;  
if first.usubjid then do;  
    hb0 = base;  
    hb11 = .;  
    hb15 = .;  
end;
```

```
if avisit = 11 then hb11 = aval;  
if avisit = 15 then hb15 = aval;  
if last.usubjid then output;  
run;
```

Step 2.

```
/** step 2: Create monotone missingness using MCMC  
imputation */  
proc mi data=analysis seed=24637883 nimpute=1  
out=outdata1;  
mcmc impute=monotone;  
var hb0 hb11 hb15;  
run;
```

Step 3.

```
/** step 3: Perform PMM regression imputation */  
proc sort data=outdata1;  
run;  
  

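### Values filled in to make missingness monotone are drawn once and shared by all 30 imputations, so the pooled SE is somewhat too small; for titer and HbA1c the code also contradicts its own text

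*SAP*

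**What the plan says.** **Titer, SAP 10.1.2.** Step 2 of the list says: "Run 30 Markov Chain Monte Carlo (MCMC) imputations to make the missing" values monotone, giving one record per imputation per subject. Step 3 says: "Run a pattern mixture model regression imputation on each imputed dataset from Step 2". The Step 2 code reads "proc mi data=analysis seed=41671703 nimpute=1" and the Step 3 code reads "proc mi data=outdata1 seed=41671703 nimpute=30". Neither version of Step 3 (at least 6, or fewer than 6, retrieved dropouts per arm) has `BY _imputation_`.

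**HbA1c, SAP 10.1.4.** The text of the two steps is the same. The code reads "proc mi data=analysis seed=24637883 nimpute=1", followed by 30 imputations of that one data set, by treatment only.

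**Binary ADA, SAP 8.7.2.1 and 10.1.1.** The method text says: "A monotone missingness pattern will be created by taking a random draw from the binomial distribution". Step 2 in 10.1.1 gives no count. The code writes one value per flagged cell, "RESP&visit=ranbin(86537043,1,&mylrate" for MYL-1601D and a matching call for NovoLog, into the data before the 30-fold logistic imputation. SAP 8.7.2.1 also says in general: "Each imputation will be repeated 30 times with a seed of 40872021 for ADA binary response", and the same for titer.

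**Combination, SAP 10.1.3.** Each path must deliver 30 records per subject. The text expects a subject's TEAR status to be able to differ between imputations.

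**Missing-data rate.** None is given. Protocol 7.1 makes no allowance for attrition and relies on imputation to keep every subject in the primary analysis.

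**The concern.** PROC MIANALYZE measures the uncertainty due to missing data by how far results differ across the 30 data sets. A value filled once and copied into all 30 does not differ, so it is counted as if it had been observed. The pooled SE is then too small, the 90% CI too narrow, and equivalence a little easier to declare than two one-sided tests at 5% allow.

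On the binary path one draw can settle a subject's outcome. Any positive post-baseline visit makes a baseline-negative subject TEAR positive, so a single filled value of 1 fixes that subject as positive in all 30 data sets.

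For titer and HbA1c there is a practical hazard as well. A programmer who follows the text in Step 2 and the code in Step 3 would feed 30 stacked copies of every subject into one PROC MI call.

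**Working it through.** **1. The plan's own figure.** SAP Table 2 and the code in SAP 10.2 give margin = (z0.95 + z0.90) × √(2p(1−p)/250). With z0.95 + z0.90 = 2.926:
- p = 5%: 2.926 × 0.01949 = 5.7%
- p = 30%: 2.926 × 0.04099 = 12.0%
- p = 50%: 2.926 × 0.04472 = 13.1%

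All 12 rows reproduce to within 0.05 points. The margins are not in question. The point concerns the CI that is set against them.

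**2. Text against code for the monotone step.**

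| Path | Text | Code |
|---|---|---|
| Titer | 30 draws, then one regression imputation on each | 1 draw, then 30 on it |
| HbA1c | 30 draws, then one regression imputation on each | 1 draw, then 30 on it |
| Binary ADA | one random draw; general statement of 30 in 8.7.2.1 | 1 draw, then 30 on it |

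**3. Effect on the variance.** Rubin's rules give T = W + (1 + 1/30)B. A fill common to all 30 data sets adds nothing to B.

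**4. Upper bound.** Let a share m of subjects have a TEAR status that rests wholly on one draw from the observed rate p (q = 1 − p). In one arm the true variance is (pq/n)[1/(1−m) + m], and the reported variance is pq/n. The true SE is √(1/(1−m) + m) times the reported SE. The one-sided error is 1 − Φ(1.645/ratio). With 30 separate fills the reported CI would be √(1 + (31/30)m) times as wide.

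| m (assumed) | True/reported SE | 90% CI coverage | One-sided error | Width, 30 fills/1 fill |
|---|---|---|---|---|
| 2% | 1.020 | 89.3% | 5.3% | 1.010 |
| 5% | 1.050 | 88.3% | 5.9% | 1.026 |
| 10% | 1.101 | 86.5% | 6.8% | 1.050 |

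**5. Simulation of the steps.** 250 subjects per arm, 30 imputations, 10% dropout, all subjects placed on the path being studied. The missing rates and within-subject correlations are assumptions. Figures are 90% half-widths in percentage points.

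| Step | Intermittent gaps per visit | 1 fill | 30 fills | Too narrow by |
|---|---|---|---|---|
| Titer (TEAR about 26%) | 2% | 6.55 | 6.58 | 0.5% |
| | 5% | 6.61 | 6.65 | 0.7% |
| | 10% | 6.65 | 6.74 | 1.5% |
| | 20% | 6.70 | 6.90 | 2.9% |
| Binary, flag as coded (TEAR about 35%) | 2% | 7.24 | 7.44 | 2.8% |
| | 5% | 7.42 | 7.63 | 2.8% |
| | 10% | 7.72 | 7.96 | 3.0% |
| Binary, filling intermittent gaps (TEAR about 35%) | 2% | 7.29 | 7.46 | 2.3% |
| | 5% | 7.39 | 7.78 | 5.1% |
| | 10% | 7.52 | 8.21 | 8.4% |

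For the binary step as coded, coverage was 88.5, 89.9 and 86.4% with one fill, against 90.7, 89.9 and 88.7% with 30. The binary runs had 800 replicates each, so coverage is known to about 1 point. The titer runs had 60 replicates with model parameters taken as known, so only their widths are used.

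**6. Against the margin.** At a 35% reference rate the margin is 12.5 points. In the 5% as-coded row, equivalence passes for an observed difference up to 12.5 − 7.42 = 5.08 points with one fill and 12.5 − 7.63 = 4.87 with 30. The pass limit moves by about 0.2 points.

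**7. Which binary cells are filled.** In SAP 10.1.1 Step 2, the flag is 0 when a later value exists and 1 when none does, and cells flagged 1 are filled at visits 8 to 13. As written, this fills a dropout's trailing visits and leaves intermittent gaps open. The step's stated aim is a monotone pattern, which requires the opposite.

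**The case against.** The strongest reply is that the appendix is headed as example code. For titer and HbA1c the prose already states a sound procedure, and a programmer could follow it. The flow chart added in SAP version 3.0 is not visible here, so the intended sequence cannot be fully checked. These points limit the finding but do not remove it. The code is the only detailed specification of the primary imputation that can be read, and it departs from its own text.

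The titer effect is probably small, and this stands. Only intermittent gaps are filled, only in baseline-positive subjects, and only where other visits do not already decide TEAR. The simulation treated everyone as baseline positive and still found at most 3%.

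Four stronger readings are tempting but not supported:
- A reader might infer that the text asks for 30 binary fill-ins. The step text asks for one random draw. Only the general sentence in SAP 8.7.2.1 points to 30, so this part criticises the method and is not a plain conflict of text and code.
- A reader might take 5.3, 5.9 and 6.8% as the trial's error rates. They assume that TEAR status rests wholly on the single draw. Visit 15 is still imputed 30 times and can change a dropout's status, and m is not the dropout rate.
- A reader might extend the equivalence argument to HbA1c. That analysis is a sensitivity analysis of a secondary endpoint with a 95% CI and no equivalence test.
- A reader might take the filling of dropouts' visits 8 to 13 as intended. It follows from the literal flag, which contradicts the purpose of the step and is an error in its own right.

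**Conclusion.** The defect is real and should be corrected. Titer and HbA1c code contradicts the text above it. On all three paths the monotone fill-in is shared by all 30 data sets and adds no between-imputation variance. The direction is certain: the pooled SE is too small, and the 90% CI for the TEAR difference is somewhat too narrow.

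The size is modest and conditional. With no missing-data rate in the documents, the figures rest on assumed rates: about 0.5 to 3% too narrow for titer (gaps of 2 to 20% per visit) and about 3% for the binary step as coded at 10% dropout. If the binary step filled intermittent gaps instead, as its aim implies, the figure would be about 2 to 8% for gaps of 2 to 10% per visit. In the trial, subjects divide between the two paths, whereas each simulation put all of them on one. The one-sided errors in the bound are ceilings for the stated shares, not estimates. For HbA1c only the 95% CI of a secondary sensitivity analysis is affected.

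**What to change.** **Titer and HbA1c.** Run the MCMC monotone step with `nimpute=30`. Then run Step 3 with `nimpute=1` and `BY _imputation_`, keeping BY treatment wherever the code already has it, since SAP 7.2.1 calls for imputation within the same treatment group. This restores the SAP's written method.

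**Binary ADA.** First correct the flag, so that a gap is filled when a later value exists and trailing gaps are left to the logistic model. Without this, repeating the draw would fill the wrong cells 30 times. Then repeat the fill-in 30 times with different seeds, and run one logistic imputation per fill, carrying the same `_imputation_` number into the merge in SAP 10.1.3. Amend the step text in SAP 8.7.2.1 and 10.1.1 to say that the fill-in is repeated within each imputation.

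**Cost.** Small code and text edits; no new data.

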7.2 Handling of missing data and outliers

7.2.1 Missing data analysis methods

Missing data will only be imputed in the primary and sensitivity analyses for TEAR rate associated with ADA and other secondary variables that are mentioned in this document. Otherwise, missing data will not be imputed.

Subjects with missing data are either 1) subjects who completely miss post-baseline ADA data or 2) subjects who miss a portion of ADA data and for whom the TEAR positive or negative status cannot be determined. If a subject with partially missing ADA data already

meets the TEAR criteria, the subject is not considered to be a subject with missing data. To minimize any bias due to missing data, multiple imputation will be used to fill in missing values according to either of two TEAR criteria (binary response and continuous titer values) prior to deriving the TEAR and subsequently estimating the treatment difference and 90% confidence interval. Two imputation processes will be used for each of two TEAR criteria among the missing data. For baseline ADA negative subjects, post baseline binary response (positive or negative) will be imputed using logistic regression multiple imputation assuming missing not at random. For baseline positive subjects, missing titer values (continuous values) will be imputed with same treatment group non-missing subjects using pattern mixture model with the complete-case missing values (CCMV) method (Little 1993). In the case where there are sufficient number of retrieved dropouts, that is, if there are 6 retrieved dropout subjects in each treatment group, the missing values in that treatment group will be imputed by modelling the retrieved subgroup data. Retrieved dropout subjects are the subjects who discontinued assigned study treatment but still remain on the study and had their efficacy and safety measurements captured at the planned visits. If less than 6 retrieved dropout subjects in each treatment group, all non-missing subjects within same treatment group will be used to impute missing data by multiple imputation.

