8.7.3.1 HbA1c

HbA1c is collected at week -7 to -4 (visit 1), baseline, week 12 (visit 11), and week 24 (visit 15). The measurements are performed by the central laboratory.

Actual values and changes from baseline at each time point will be computed and summarized by treatment group. Treatment difference and 95% confidence interval will be displayed along with p-values.

A sensitivity analysis for HbA1c will be performed using multiple imputation to impute missing values with non-missing subjects within the same treatment group using a pattern mixture model with the complete-case missing values (CCMV) method (Little 1993). After imputation, treatment difference, 95% CI, and p-values will be generated using same MMRM model as above. Sample imputation code is provided in Appendix 10.1.4.

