10.1 Multiple imputation

Multiple imputation will be applied to fill in missing values for ADA binary response and for ADA titer.

For binary ADA response, if baseline ADA value is missing, the missing baseline value will be imputed (6 imputations) based on binomial distribution using probability of no missing baseline values from the same treatment group. After imputations, for subjects with negative baseline ADA (Section 10.1.1) missing post-baseline binary response (positive or negative) will be imputed using logistic regression multiple imputation. For subjects who are ADA positive at baseline (Section 10.1.2), missing post-baseline ADA continuous titer values will be imputed with same treatment group non-missing subjects using continuous MI model.

The steps are summarised below:

Section 10.1.1 describes the methodology for imputation of binary response, while Section 10.1.2 covers the imputation of continuous ADA titer, and Section 10.1.3 puts them together.

10.1.1 Multiple imputation for binary ADA response if baseline ADA is negative.

For purposes of these specifications, let $RESP_x$ represent the binary value (0 or 1) at Visit x , where x takes the values 0 (for Baseline) or 8–15. The seed that will be used in the multiple imputation of ADA binary response will be 40872021.

Missing values will be obtained from logistic regression imputation on the observed values of binary response. A fully conditional specification (FCS) method will be used to impute values from a non-monotone missing data pattern.

There are 3 steps to this process:

1. Create a dataset with one record per subject, containing all values of $RESP$ for all weeks (Baseline and Weeks 2–24 on one record); that is, each record would contain variables for $RESP_0$ and $RESP_8$ – $RESP_{15}$. The subject-level $RETRIEVED$ variable described in Section 8.7.2.1 can also be generated at this time for subjects who discontinued treatment, based on whether values after treatment discontinuation

- were retrieved (set retrieved=1) or remain missing (set retrieved=0).
2. Fill in missing values to make a monotone missing data pattern, by drawing random TEAR values from the binomial distribution based on the TEAR frequencies for the given visit within treatment group.

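### The MCMC step that fills interim titer and HbA1c gaps pools the two arms, against the SAP's same-treatment-group rule; the effect on the TEAR difference is probably small, but it is anti-conservative

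*SAP*

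**What the plan says.** The broadest statement of the rule is in SAP 10.1: for subjects who are ADA positive at baseline, "missing post-baseline ADA continuous titer values will be imputed with same treatment group non-missing subjects using continuous MI model". SAP 7.2.1 has the same rule ("missing titer values (continuous values) will be imputed with same treatment group non-missing subjects"), tied there to the CCMV pattern-mixture model. For HbA1c, SAP 8.7.3.1 plans to "impute missing values with non-missing subjects within the same treatment group".

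SAP 8.7.2.1 assigns titer gaps before the last observed visit to an MCMC step, does not mention treatment group for it, and points to Appendix 10.1 for the code. The titer code (10.1.2 Step 2) is "proc mi data=analysis seed=41671703 nimpute=1", then "mcmc impute=monotone", then "var ada0 ada8-ada15". The HbA1c code (10.1.4 Step 2) is "proc mi data=analysis seed=24637883 nimpute=1", with the same MCMC statement and "var hb0 hb11 hb15". Neither call has a BY statement or a treatment variable, although Step 1 of both sections keeps `trtp` in the dataset.

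Under 8.7.2.1 and 10.1.3, a baseline-positive subject is TEAR positive if any post-baseline titer, observed or imputed, is at least four times baseline.

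**The concern.** As coded, Step 2 fits one mean vector and one covariance matrix to both arms. A gap is then filled as if the two products had the same titer profile, apart from what the subject's own observed visits carry. If the profiles differ, filled values in the two arms are drawn toward each other.

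For titer this reaches the primary endpoint, because one filled visit can decide whether a baseline-positive subject counts as boosted. The primary test looks for equivalence, so a difference that is too small makes it easier to reject non-equivalence. For HbA1c no equivalence decision is involved; the point there is that the code does not follow the stated rule.

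**Working it through.** **1. How each imputation step treats the arms**

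| Step | SAP section | Arms |
|---|---|---|
| Binary ADA, monotone fill | 8.7.2.1; 10.1.1 Step 2 | separate rate per arm |
| Titer, MCMC fill | 10.1.2 Step 2 | together |
| HbA1c, MCMC fill | 10.1.4 Step 2 | together |
| Binary and titer regression, fewer than 6 retrieved dropouts | 10.1.1 and 10.1.2 Step 3 | BY arm |
| Binary and titer regression, 6 or more | 10.1.1 and 10.1.2 Step 3 | together |
| HbA1c regression | 10.1.4 Step 3 | BY arm |

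No text authorises pooling. The MCMC calls look like an omission.

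**2. The plan's own figures**

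Margin = (z0.95 + z0.90) × √(2p(1−p)/250), with the quantiles used in the SAP 10.2 code. At p = 0.25: 2.926 × √(0.375/250) = 2.926 × 0.03873 = 11.33%, against 11.3% in SAP Table 2. All 12 margins reproduce within 0.05 points. Power, 2Φ(margin/SE − 1.645) − 1, is 79.5-80.6% at the printed margins. None of this depends on the imputation code.

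**3. Upper bound on the error rate**

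Suppose a share m of all subjects had TEAR status drawn from the pooled arms, ignoring their own observed visits. A true difference D becomes (1 − m)D. With D at the margin and the margin held fixed, the one-sided error is Φ(mD/SE − 1.645). For a 25% reference rate, the other arm is at 36.33%, so SE = √((0.25×0.75 + 0.3633×0.6367)/250) = 0.0409.

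| m | Difference (points) | One-sided error |
|---|---|---|
| 1% | 11.22 | 0.053 |
| 2% | 11.11 | 0.056 |
| 5% | 10.77 | 0.066 |
| 10% | 10.20 | 0.086 |

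**4. Simulation of the coded step**

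The actual draw conditions on the subject's other visits, so the real effect is smaller. All inputs here are assumed:
- 60% of subjects are baseline-positive, and the rest contribute no arm difference.
- There are eight titers (baseline and seven post-baseline samples), normal on the log2 scale with SD 1.2 and AR(1) correlation 0.9 or 0.7.
- One arm is shifted by 0.8 log2 after baseline.
- Gaps fall at the six interim post-baseline visits only; 300,000 subjects per arm.

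TEAR difference in percentage points, raw titers (the code applies no transformation):

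| Gap per visit | Correlation | No gaps | Within-arm fill | Pooled fill | Within-arm minus pooled |
|---|---|---|---|---|---|
| 2% | 0.9 | 11.58 | 11.70 | 11.53 | 0.17 |
| 2% | 0.7 | 13.94 | 14.00 | 13.76 | 0.24 |
| 5% | 0.9 | 11.58 | 11.85 | 11.43 | 0.42 |
| 5% | 0.7 | 13.94 | 14.07 | 13.51 | 0.56 |
| 10% | 0.9 | 11.58 | 12.07 | 11.24 | 0.83 |
| 10% | 0.7 | 13.94 | 14.15 | 13.03 | 1.11 |

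On log titers the last column runs from 0.00 to 0.13.

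On the raw scale the within-arm fill itself runs 0.06 to 0.49 points above the complete-data value, because a normal model fits skewed titers poorly. Against complete data, the pooled fill loses 0.05 to 0.91 points (11.58 − 11.53 up to 13.94 − 13.03).

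**5. HbA1c**

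With only baseline, Week 12 and Week 24 in the model, Step 2 mainly fills a missing Week 12 value when Week 24 is present. Take a true Week 12 difference of 0.20. Under assumed correlations the filled subjects carry 0.111 of it. With gap share g the estimate is 0.20 − g(0.20 − 0.111): 0.198, 0.196 and 0.191 for g = 2%, 5% and 10%. Even if the fill carried no difference at all, it would be 0.196, 0.190 and 0.180.

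**The case against.** The case on the other side has real content.

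- **The rule is looser than it looks.** SAP 7.2.1 and 8.7.3.1 attach the same-group wording to the CCMV model, which is Step 3, and 8.7.2.1 describes the MCMC fill without naming arm. This is fair, but SAP 10.1 states the rule for missing post-baseline titers generally.
- **It is example code.** It cannot run as printed: a nine-element array is indexed 8 to 15, Step 1 keeps `trtp` while Step 3 uses BY `treatment`, and a Visit 14 titer is listed although no sample is drawn then. A programmer must rewrite it, and the flow chart is not shown. That limits certainty about the final program. It does not remove the point, because 8.7.2.1 names this appendix as the code for the primary imputation.
- **Few values may be affected.** SAP 8.1 lets unscheduled results stand in for a missing visit, and its windows are contiguous from Visit 8. A fill matters only for a baseline-positive subject who has not already met TEAR at an observed visit. This stands and keeps the effect small.

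A reader might infer that the HbA1c fill also favours an equivalence claim. The documents do not support that: the HbA1c analysis is a sensitivity analysis of a secondary endpoint, reported with 95% intervals and p-values and without a margin, and the endpoint is change to Week 24. A reader might also take a log-scale simulation as the size of the effect, but the code imputes untransformed titers, where the effect is larger.

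**Conclusion.** The conflict is real. Both Step 2 MCMC calls pool the arms, the text calls for same-group imputation, and nothing permits pooling. For titer the bias is toward no difference whenever the arms differ, so it is anti-conservative for the primary test.

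The size is probably small and cannot be fixed from the documents, which give no gap rate and no baseline-positive share. Under the assumptions above, the pooled TEAR difference is about 0.2-1.1 points below the within-arm result on raw titers and at most about 0.13 points below on log titers, on a true difference of 11.6-13.9 points. The error rates of 0.053-0.086 are an upper bound that ignores each subject's own data. They should not be read as the expected error of this trial, and the point does not show that an equivalence conclusion would be overturned.

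For HbA1c the matter is consistency with the stated rule, and it mainly touches the Week 12 contrast. This is worth correcting because the remedy simply carries out what the SAP already says.

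**What to change.** - In 10.1.2 and 10.1.4, sort by the treatment variable kept in Step 1 (`trtp`) and add a BY statement for it to both Step 2 MCMC calls. Use one name throughout: the appendix now uses `trtp`, `trtgroup`, `treatment` and `trt`, and the binary Step 1 keep list carries no treatment variable at all.
- Correcting Step 2 alone would leave the calls for six or more retrieved dropouts pooled. Make those calls within-arm as well, for titer and binary ADA, with BY or a treatment term. At the threshold of 6 per arm, a by-arm regression of the Week 24 titer on seven earlier samples plus an intercept has 8 coefficients for 6 subjects, so the choice needs to be stated.
- State in 8.7.2.1 that the MCMC fill is done within treatment group.

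The cost is a few lines of code and one sentence of text. Table 2, the sample size and the power are unchanged. The number of draws in Step 2 and the scale on which titers are imputed are separate questions; the BY statement does not settle them.
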